Study outcomes	
The main outcomes of this study are
 
 1) The change of baseline glycated hemoglobin (HbA1c) among prediabetes adults at 6 months. 2) The change of baseline fasting plasma glucose (FPG) among prediabetes adults at 6 months. 3) The change of baseline 2-hour post-load plasma glucose among prediabetes adults at 6 months. 4) The change of baseline continuous glucose monitoring (CGM) profile among prediabetes adults at 6 months. 
Secondary outcome of this study are
 
 1) The change of eating misalignment among prediabetes adults at 6 months. 2) The change of chronotype among prediabetes adults at 6 months.
Sample Size	120 prediabetic individuals
Study Duration	1 March 2022 until 31 December 2023
Name and Address of Sponsor	Fundamental Research Grant Scheme (FRGS), Ministry of Higher Education/ UMalaya (FRGS/1/2021/SKK06/TARUC/02/1)

Ethics Approval	Tunku Abdul Rahman University Management and Technology Ethics Committee (TAR UC/EC/2021/02-3) Medical Research and Ethics Committee (RSCH ID-21-00114-IVI)
-----------------	---

Executive Summary:

Early meal timing affects the circadian rhythmicity and influenced the postprandial blood glucose level in response to meal in diabetes patients. In the other words, diabetes patients with earlier meal timing had a stable glycemic control compared with those with late meal timing. This is a new concept to switch the meal timing earlier than later in diabetes self-monitoring management. However, there is insufficient evidence from Southeast Asia to determine the optimal-meal-timing and its association with glycemic measures in prediabetes individuals. Hence, this study carried out to determine the associations of chronotype and chrononutrition with glucose tolerance among prediabetic individuals in Malaysia.

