
3.1.1 Meal intakes timing of ingestion: morning versus dinner

Evidence suggests that meal ingestion in the morning and late evening (time of day) influence glucose metabolism in humans. Earlier studies, using mixed meals or glucose infusion, have reported circadian responses of reduced glucose tolerance and insulin sensitivity in healthy participants for the evening rather than in the morning (Almoosawi et al. 2016). An acute study which examined the effects of a late evening meal on diurnal variation of blood glucose in healthy individuals, assessed by continuous glucose monitoring (CGMS™). There was an increase in blood glucose after the late evening meal which shifted towards later at night, with peaking of blood glucose observed during sleep (Astiz et al. 2019). Late evening meals may cause postprandial hyperglycaemia with this decrease in glucose tolerance from morning towards the night. A cohort study was the first to show the relationship between late-night dinner consumption and glycaemic control in type 2 diabetics, whereby having a late dinner meal after 8 pm was independently associated with an increase in HbA1c (Sakai et al. 2018). In some acute trials, both healthy individuals (Kajiyama et al. 2018) and type 2 diabetics (Imai et al. 2017) showed significantly higher blood glucose and insulin values after night-time meals. These studies deduce that the disruption of the circadian rhythm led to the exacerbation of the physiological nocturnal decrease of glucose tolerance. Peter et al. showed that type 2 diabetic subjects who ate three identical meals had glucose excursions that were higher in the morning than in the evening (Sakai et al. 2018). There was increased glucose tolerance in response to the first and third meals of the day, irrespective of glycaemic control. There was also a change in circadian variation in insulin sensitivity in type 2 diabetics (Sakai et al. 2018). Type 2 diabetics exhibit a different daily circadian pattern from healthy individuals, with increased insulin sensitivity towards the night, and higher glucose excursions in the morning than in the evening. Methods to improve glycaemic control at dinner has been reported by some authors. Dinner that was divided into two smaller meals reduced post-meal glycaemic excursions, due to the “second-meal effect” phenomenon, by enhancing β -cell responsiveness (Karthikeyan et al. 2018) at the second dinner meal induced by the first meal (Imai et al. 2017). It was also suggested that if meal size and carbohydrate quantities were smaller, postprandial glucose can be ameliorated in both healthy and type 2 diabetics. In summary, time of day is indicative of having an influence on the postprandial glucose response to a meal. There is a defined circadian pattern for postprandial glycaemia for similar meals consumed either in the evening or morning. Glucose metabolism is not only affected by what and how much you eat alone, but also when the meal is consumed. However, more data from well-designed epidemiological studies is necessary to prove causality. Mezitis & Bhatnagar (2018) emphasize the importance of chrononutrition in people with diabetes because even insulin sensitivity has been shown to exhibit circadian rhythmicity. Glycemic responses to meals are exaggerated in these individuals, more so when the meal is timed to be consumed out of sync with the metabolic pacemaker (Almoosawi et al. 2016). Accordingly, Mezitis & Bhatnagar (2018) recognize optimal hormonal and hepatic function beginning in the early morning (4:00 a.m.) and fading in the early evening (4:00 p.m.). Review of glucose records—increasingly more abundant in the era of continuous glucose monitoring (CGM), which permits review of several months of

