The sample size is estimated using G*Power software version 3.1.9.4 (Erdfelder, Faul and Buchner, 1996). To determination of association between chrononutrition and glycemic control, the β -coefficient of 0.13 adopted from Sakai *et al.*, (2018), the power was set to 0.9 with 2 sided significance level and alpha error given 0.05, a total of 83 prediabetic adults expected in this study. To compensate for the non-responding and non-compliance during follow-up, a dropout rate of 50% will be considered, the total sample size required is 166 subjects in the study for 6 months.

Test Family: T Test

Statistical Test: Linear Multiple Regression Fixed Model, single regression coefficient

Tail(s): 2

Effect Size (β -coefficient): 0.13 (Sakai *et al.*, 2018)

α Error prob: 0.05

Power(1- β err prob): 0.90

[figure not shown]
Total Sample Size: 83 prediabetes individuals

50% dropout rate taken as consideration in study for 6 months follow up, total 166 prediabetes individuals shall be recruit in this study.

Dropout Rate:

$$= \frac{83}{1-0.5} = 166 \text{ prediabetic individuals}$$

Figure 3: Flow diagram of the study design

Participants will be undergoing OGTT, FBS and HbA1c tests after an overnight fast of 8-10 hours. This is a routine universal test for prediabetes/ diabetes diagnosis. Participants will be informed to eat their usual diet for three days prior to the test. The diagnostic value for diabetes on plasma glucose. the diagnostic values for prediabetes and diabetes based on OGTT, and the diagnostic values for prediabetes and diabetes based on HbA1c have been shown in Table 1, Table 2 and Table 3, respectively. Fasting blood sample will be taken for FBS and HbA1c tests. Subsequently, participants will be given 75-gram glucose water to drink within 5 minutes. Blood sample will be taken after 2 hours for glucose determination. Participants should rest throughout test with only plain water is allowed to drink. Figure 4 shows the procedure of OGTT. All the tests will be conducted in the healthcare clinic lab. Results will be traced from medical record.

Table 4: Summary of data collection and timeline

Data	Baseline	3 months	6 months
Sociodemographic			
Age	.	.	.
Date of Birth	.	.	.
Marital Status	.	.	.
Education Level	.	.	.
Occupation	.	.	.
Monthly Household Income	.	.	.
Health History	.	.	.
Smoking Habit	.	.	.
Supplementary Consumption	.	.	.
Anthropometry			
Weight	.	.	.
Height	.	.	.
Waist Circumference	.	.	.
Visceral Fat	.	.	.
Body Fat	.	.	.

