pattern from the validated questionnaires PSIQ and light exposure from the validated questionnaire HLEQ.

Statistical Analysis

All data will be performed statistical analysis using the SPSS software version 20 (SPSS Inc., Chicago, IL, USA). The socio-demographic will be presented as mean, standard deviations, median, interquartile range, frequency, and percentage. Data cleaning will be performed to exclude the outlier data before the normality is checked using Kolmogorov-Smirnov Test. The investigator considered $p < 0.05$ to be statistically significant. Chronotype, sleep quality, and light exposure will be analyzed as categorical variables whereas dietary intake, chrononutrition, anthropometry, glycemic measure, and physical activity will be analyzed as continuous variables.

The investigator will perform a multivariable generalized linear model to examine the association between night meal pattern (last night mealtime either dinner or supper with calories intake, frequency of night snacking, and the total number of the night snacking) and glycemic outcome (HbA1c, FPG, 2hPPG, CGM profile) by adjusting for the potential covariates. Specifically, nighttime will be characterized by the time range from 1900 and 0659 hours based on Malaysia solar time. The investigator will explore the late-night meal timing in 2000, 2100, and 2200 to examine its association with glycemic outcomes. The potential confounders include sociodemographic characteristics, physical activity, sleep pattern, sedentary behavior, diet quality, and light exposure will be controlled. ANCOVA test will be performed to understand the association between chrononutrition (breakfast skipping, meal frequency, eating window, sleep timing, chronotype, and fasting pattern) with glycemic variables, controlling for potential covariates (sociodemographic characteristics, light exposure, diet quality, physical activity and sleep pattern).

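### Four unranked main outcomes and three late-meal times are examined at p < 0.05 with no primary test or multiplicity rule; read as 12 tests, the chance of a false late-eating result is roughly 20–43%

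*Combined protocol and SAP*

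**What the plan says.** **Outcomes.** The synopsis (Study outcomes) opens its list with "The main outcomes of this study are" and names four: change from baseline to 6 months in HbA1c, fasting glucose, 2-hour post-load glucose and the CGM profile. The Study Outcomes paragraph in section 3 gives the same four domains, with glucose variability as the CGM component. Neither place ranks them, and no single CGM metric is chosen.

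**Analysis.** Section 3, Statistical Analysis, fits the night-meal model to all four outcomes and adds: "The investigator will explore the late-night meal timing in 2000, 2100, and 2200 to examine its association with glycemic outcomes". The only error rule is "The investigator considered $p < 0.05$ to be statistically significant". The same section says that chrononutrition variables are analysed as continuous.

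**Sample size.** Section 3, Sample size Calculation, specifies "Statistical Test: Linear Multiple Regression Fixed Model, single regression coefficient", and "the power was set to 0.9 with 2 sided significance level and alpha error given 0.05". Its inputs and result are "Effect Size (β -coefficient): 0.13" and "Total Sample Size: 83 prediabetes individuals". It does not say which outcome or which exposure that coefficient belongs to.

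**Source of the effect size.** Literature review section 3.1.1 reports, from the cohort that supplies the 0.13, that "having a late dinner meal after 8 pm was independently associated with an increase in HbA1c".

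**The concern.** The study is sized for one test but plans many, and nothing in the plan says which one carries the conclusion. Section 3 states a directional hypothesis that earlier meal timing goes with lower glycaemia. The CGM description says the data will be used to find an optimal meal time, and the summary of the literature review expects the findings to steer clinical guidelines. The three late-meal times are the part of the analysis most likely to yield such a clock time. With no time and no outcome fixed in advance, whichever combination gives the smallest p-value could be reported as the optimum, although a nominally significant one is fairly likely to arise by chance.

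**Working it through.** **1. Reproduce the plan's own figure.** For one coefficient, the noncentral t test has noncentrality √(f² × N). With f² = 0.13, two-sided alpha 0.05 and power 0.90:

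- N = 83, with power 0.901. The result is 83 for 1 to 6 predictors and 84 for 10.
- The 0.13 is labelled a β-coefficient, but it gives 83 only when entered as Cohen's f². Entered as R² it gives 73, and as a correlation 614.
- Dropout: 83 / (1 − 0.5) = 166, as stated.

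So 83 covers exactly one test at 0.05.

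**2. Count the tests.** Four outcomes × three times = 12, if each time is a binary split tested separately.

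**3. Independence ceiling.**

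- Three times alone: 1 − 0.95³ = 14.3%
- Four outcomes alone: 1 − 0.95⁴ = 18.5%
- All twelve: 1 − 0.95¹² = 46.0%

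**4. Allow for dependence.** The three splits cut the same variable and the four outcomes all measure glycaemia, so the tests are correlated. The documents give neither the distribution of last-meal time nor the outcome correlations. Both are assumptions here. The simulations use n = 83, no true association, a normal last-meal time split at 20:00, 21:00 and 22:00, four equally correlated outcomes, and two-sided tests at 0.05.

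| Outcome correlation | Chance of at least one p < 0.05 (mean last meal 20:00–21:00, SD 1–1.5 h) |
|---|---|
| 0 | 41–44% |
| 0.3 | 38–42% |
| 0.5 | 35–37% |
| 0.7 | 30–32% |
| 0.9 | 22–25% |

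Other meal-time assumptions, as the outcome correlation rises from 0 to 0.9:

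- Mean 20:30, SD 1.2 h: 43% falling to 24%.
- Mean 20:00, SD 1 h: 39% falling to about 20%.
- Mean 19:30, SD 1 h (few late eaters): 33% falling to 18%.

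Rounded, the range is 20–43%. A generic 12-test grid with correlation 0.9 among both the times and the outcomes gives 15%, the lowest value found.

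**5. Direction.** These figures count false results in both directions. Under independence, the chance of at least one in the hypothesised direction is 1 − 0.975¹² = 26%. For mean 20:30 and SD 1.2 h it is about 25% at outcome correlation 0 and 12% at 0.9, roughly half the two-sided figure.

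**6. Cost of a blanket correction.** Again with f² = 0.13:

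| Approach | Alpha per test | Power at N = 83 | N for 90% power |
|---|---|---|---|
| One named primary test | 0.05 | 90% | 83 |
| Bonferroni over 4 outcomes | 0.0125 | 77% | 114 |
| Bonferroni over 12 tests | 0.00417 | 63% | 137 |

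Naming one test keeps the planned sample size.

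**The case against.** The strongest reply is that the 12-test count is an inference. The plan says it will *explore* the three times. It does not say that it will fit three binary splits, and categories within one model would fit the wording as well. Because chrononutrition is to be analysed as continuous and the night-meal model uses last mealtime, the main analysis may already be continuous, with the clock times as exploration around it. In a convenience-sample observational study, formal family-wise control is also debated, and clear labelling with full reporting may be enough.

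Much of this stands. The binary-split reading is reasonable but not explicit, and the percentages depend on it. It does not remove the gap, because on any reading no primary outcome, exposure form or order of testing is named. The guideline ambitions also make it hard to treat the clock-time results as exploration only.

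Two stronger readings are tempting, and the documents support neither:

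- **A promised 5% is broken.** The 5% is a per-test threshold and the alpha of one power calculation. No family-wise rate is claimed anywhere.
- **The error rate is 46%.** That needs twelve independent tests, which three splits of one mealtime cannot give.

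The 12 are also not the whole late-eating family. Night-snacking frequency and number, an unspecified CGM metric and a logistic model of early versus late mealtime on diabetes incidence would add tests.

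**Conclusion.** The concern holds as a gap in specification. Four unranked outcomes, three late-meal times and a flat p < 0.05 sit beside a sample size for one coefficient, with no rule linking them. Under the 12-test reading, the chance of at least one false late-eating result is roughly 20–43%, and about half that in the hypothesised direction. The figure rests on assumed meal-time distributions and on outcome correlations of 0 to 0.9, none of which the documents give. It was well above 5% in every scenario tried, the lowest being 15%. The plan should be changed, but the gap does not invalidate the study.

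**What to change.** In section 3, Statistical Analysis:

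1. **Name one primary test:** 6-month HbA1c, adjusted for baseline HbA1c, on last-meal clock time as a continuous variable. With baseline in the model, the exposure coefficient is the same as for change in HbA1c, so this agrees with the synopsis. It also follows the plan's own rule on continuous chrononutrition variables, and HbA1c is the outcome reported from the cohort that supplied the effect size. That cohort's exposure was dinner after 8 pm, so only the outcome carries over.
2. **Define the exposure scale.** Keep last meals before 19:00 on the same continuous scale.
3. **Handle the other main outcomes.** Test fasting glucose, 2-hour glucose and one named CGM metric with Holm, or label them supportive.
4. **Report 20:00, 21:00 and 22:00** as predicted values from the one model, not as separate tests.
5. **State what was known when.** The document is dated 6 May 2024, while section 4 schedules data entry and analysis from 07/03/2024. Say whether outcome data had been examined before the primary test was named. If they had, do not call it confirmatory.

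This is a cheap improvement: it changes analysis wording, plus the disclosure in item 5, and needs no extra participants. The downside is fewer nominally significant secondary results.

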
an extreme evening chrono-type, the circadian phase of biological rhythms could be shifted by as much as much as 2-3 hours compared with that of an extreme morning chrono-type (Kantermann et al. 2015). This shift can result in a desynchronization between the period of biological night, as regulated by the intrinsic circadian clock system, and the environmental night governed by the light-dark cycle (Kantermann et al. 2015). Patients with T2DM, later chrono-types and evening preferences have been found to be associated with poorer glycemic control (Brady et al. 2019). A recent study revealed that evening type was associated with an increased risk of having type 2 diabetes in prediabetes individuals (Anothaisintawee et al. 2017). These data may demonstrate the contribution of circadian regulation on reversing prediabetes from developing T2DM in the future.

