3. RESEARCH METHODOLOGY

Hypothesis:

The morning chronotype and early meal-timing are associated with low glycemic outcome among prediabetic individuals.

Research Questions:

Is the morning chronotype and early meal-timing are associated with better glucose tolerance among prediabetic individuals?

General objective:

To determine the associations of chronotype and chrononutrition with glucose tolerance among prediabetic individuals in Malaysia.

Specific objectives:

1. To examine the associations among chronotype, chrononutrition and glucose outcomes.
2. To investigate the association between lifestyle factors (physical activity level, light exposure, diet timing, sleep pattern) and chrononutrition.
3. To investigate the association between anthropometry measurements and glycemic outcomes.

Description of Methodology:

Participants will be recruited using the convenience sampling method. The proposed study will be conducted in community clinics in Malacca, Malaysia. Malacca is the capital of the coastal state, located in southwestern Malaysia, with an estimated total population of 0.93 million in the year 2019 (Department of Survey and Mapping Malaysia, 2021). In 2019, National Health and Morbidity Survey reported that 17% of Malaccan adults had hyperglycemia and 13.7% of them had known diabetes. Malacca is 1 out of the top five states showing the highest prevalence of diabetes in Malaysia (IPH, NIH and MOH, 2019). Permission to carry out data collection has been granted by the Medical Research and Ethics Committee (MREC) (RSCH ID-21-00114-IVI). The study protocol has been reviewed and approved by the Tunku Abdul Rahman University College (TARUC) research ethics committee (TAR UC/EC/2021/02-3).

During the process of recruitment, a trained research assistant (one of the co-researcher), clinical dietitian (one of the co-researcher) or family medicine specialist

(one of the co-researcher) will inform potential prediabetic individuals research protocol verbally and written information will be provided. Newly diagnosed prediabetic individuals who are agreeable to participate will provide written informed consent. Baseline and follow up appointments will be determined based on the community clinic appointment schedules. Those who decline to participate will continue to receive their routine treatment as usual, and care provided to each prediabetic individual will not be affected by the decision to either participate or not participate in the study.

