research assistant using the following questionnaire including (1) Munich Chronotype Questionnaires (MCTQ) (Appendix D), (2) Pittsburgh Sleep Quality Index Questionnaire (PSQI) (Appendix H), (3) Harvard Light Exposure Questionnaire (HLEQ) (Appendix G), (4) International Physical Activity Questionnaire (IPAQ) (Appendix C) and (5) Chrononutrition Profile Questionnaire (CPQ) (Appendix I). Anthropometry measurements including body fat, height, body fat percentage, visceral fat, waist circumference and hip circumference will be measured. Participants are requested to fill up 3-days dietary record (3DDR) (2 weekdays and one weekend day) and the data will be collected in the next visit. Baseline reading of fasting plasma glucose (FPG, OGTT, liver function, and HbA1c) will be retrieved from medical records in the community clinic. Routine treatment will be provided as usual. To minimize the loss of follow-up, phone conversations will be made to ensure the 3-days dietary data is completed.

At the second visit (three months from the baseline), all participants are required to wear a CGMS sensor at the back of their upper arms to measure the 24 hours glucose fluctuation over 14 consecutive days. 3DDR will be given to participants to record their consecutive 3 days dietary record and will be returned after 14 days. After 14 days, participants will return the CGMS sensor at the community clinic. Or alternative way of CGMS sensor collection by an assistant at the participant's home. All questionnaires will be interviewed by a trained research assistant again. Anthropometry measurements including body fat, height, body fat percentage, visceral fat, waist circumference and hip circumference will be measured repeatedly.

At the third visit (six months from the first visit), for FBG, OGTT and HbA1c test, all the readings will be retrieved by the research assistant from the medical record to document the glycemic outcome. The participants will be interviewed by the trained research assistant during all clinic visits using similar questionnaires. All anthropometry measurements (body fat, height, body fat percentage, visceral fat, waist circumference and hip circumference) will be conducted again. 3DDR will be given to record their 3 days dietary intake again and the record progress will be followed up through phone. The original 3DDR will be collected at the routine appointment.

Sample size Calculation:

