Anthropometric measurements (Appendix J) will be measured at the first, second and third visit. Body weight, body fat percentage and visceral fat of each participant will be measured twice using a body fat analyzer (HBF-375, Karada) and recorded to the nearest 0.1 kg, 0.1 % and 1 unit, respectively. Participants will be weighted with their minimal cloths on, barefoot, without belt and emptied pockets. They will be asked to stand still with the body weight equally distributed on both feet. Participants have to be in the Frankfurt plane, where the body is upright, upper limbs are at the body's sides with the palms facing forward, feet flat and directed forward, directly facing the researcher assistant. The height of each participant will be measured twice using a SECA portable stadiometer Model 217 (SECA GmbH & Co., Hamburg, Germany) attached to a smooth wall and recorded to the nearest 0.1 cm. Participants will be asked to stand erect, in their bare feet, with their heels, buttocks, head and shoulder blades in a vertical line against the wall. Height will be measured in the upright position against a vertical scare and with the head positioned so that the top of the external auditory meatus is in the level with the inferior margin of the bone orbit. Waist and hip circumferences of the respondents will be measured twice, according to the standardized protocol by the WHO (2008). Waist circumference will be measured at the approximate midpoint between the lower margin of the last palpable rib and the top of the iliac crest. Hip circumference will be measured around the widest portion of the buttocks, with the tape parallel to the floor. For both measurements, the participants should stand with feet close together, arms at the side and body weight evenly distributed, and should wear little clothing. Both waist and hip circumferences will be measured to the nearest 0.1 cm by using a Lufkin tape model W606PM (Apex Tool Group, Sparks, MD, USA). The reported measurements are the average values from both readings.

Study Outcomes

The main outcome of the study is the glycemic outcome including FPG (mmol/L), 2hPPG (mmol/L), HbA1c (%), and glucose variability from CGMS. The secondary outcomes are chronotype from the validated questionnaire MCTQ, and chrononutrition from the validated questionnaire CPQ, 3 days dietary record, anthropometry measurements, physical activity level from the validated questionnaire IPAQ, sleep

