To investigate the association of physical activity (MET score and steps count), sedentary behaviors (MET score), sleep pattern (sleep duration), diet quality (distribution of total energy, carbohydrate, protein, and fat), and light exposure (timing responded to a different type of light) with glycemic outcome, the multivariable generalized linear model will be conducted. Meanwhile, anthropometric measures (body mass index, body fat, and waist circumference) will be categorized as either normal or overweight and obesity group, followed by using logistic regression to examine the association between anthropometry status and glycemic outcome (non-diabetes or diabetes). In addition, the glycemic outcome will be categorized into diabetes incidence (diabetes and non-diabetes) to determine the participants who had been diagnosed with diabetes at 6 months. A logistic regression test will be used to examine the association between early and late-night mealtime and diabetes incidence.

Quality control

To ensure that the database accurately reflects the data reported in the questionnaires, a pre-test will be carried out. The research assistant trained to conduct the study procedures included interviewing administrative questionnaires, CGMS device, 3 days dietary record, and pedometer. Monthly meetings are held with the principal

investigator to review study procedures and progression. A monthly report will be documented after the meeting.

Data monitoring and management

Participants are anonymized and assigned with a specific ID at study entry. To ensure accuracy and completeness of data entry, data are checked by identifying if there is any outlier or missing value. The data checking process is performed in the first, third and sixth month of the data collection, such that the experience gained can be used to train the research assistant for improvement. Paper documents are kept in a locked cabinet and electronic data are stored on password-protected computers which can only be accessed by research team members. All records will be kept for at least 5 years after completing the study. After 5 years, all papers will be shredded using an office shredder. Extra care should be taken with sensitive or confidential information and a secure paper destruction service bin used. Digital data will be destroyed by deleting or overwriting information and destroying the physical media, such as CD rom.

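### The night-meal model does not adjust for chronotype, so part of any late-meal association with glycaemia may reflect chronotype

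*Combined protocol and SAP*

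**What the plan says.** The hypothesis in Research Methodology has two exposures: "The morning chronotype and early meal-timing are associated with low glycemic outcome among prediabetic individuals".

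The Statistical Analysis section spreads them over separate models.

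- **Night-meal model.** A multivariable generalized linear model examines the "association between night meal pattern (last night mealtime either dinner or supper with calories intake, frequency of night snacking, and the total number" of night snacks, against HbA1c, fasting glucose, 2-hour glucose and the CGM profile. Its adjustment set is: "The potential confounders include sociodemographic characteristics, physical activity, sleep pattern, sedentary behavior, diet quality, and light exposure will be controlled".
- **ANCOVA.** Chronotype is an exposure here, within "chrononutrition (breakfast skipping, meal frequency, eating window, sleep timing, chronotype, and fasting pattern) with glycemic variables". Neither the exposures nor the covariates of this model include last night mealtime.
- **Mealtime and diabetes incidence.** A logistic regression of early versus late night mealtime names no covariates.

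Chronotype and sleep pattern have different instruments. Under Study Outcomes, "The secondary outcomes are chronotype from the validated questionnaire MCTQ", while sleep pattern comes from the Pittsburgh sleep-quality questionnaire. For another model, the analysis section glosses the latter as "sleep pattern (sleep duration" in brackets. Chronotype is available at baseline, because enrolled participants are interviewed by a trained "research assistant using the following questionnaire including (1) Munich Chronotype Questionnaires (MCTQ", Appendix D).

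Section 3.2 of the literature review says that evening types usually go to bed later. It also says: "Patients with T2DM, later chrono-types and evening preferences have been found to be associated with poorer glycemic control". It then cites a study in prediabetes that links evening type to a higher risk of type 2 diabetes.

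**The concern.** On the plan's own account, chronotype is associated with the outcome and with a later evening schedule. A variable that plausibly delays the last meal and is also linked to glycaemia can confound the mealtime coefficient. It is measured at baseline but is not named in the model that tests mealtime.

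The study aims to identify an optimal meal timing and to inform the Malaysian clinical practice guideline. That use needs a mealtime association that can be told apart from an association with chronotype. As listed, the night-meal model reports a mealtime coefficient that mixes the two to an unknown degree, and no other listed model separates them.

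**Working it through.** **1. The plan's own figure.** The Sample size Calculation uses a two-sided t test of one coefficient in a linear multiple regression, with alpha 0.05, power 0.90 and effect size 0.13. For N participants and p predictors, the noncentrality is √(f²·N) with N − p − 1 degrees of freedom.

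- With 0.13 taken as Cohen's f², N = 83 gives power 0.900-0.901 for 1 to 8 predictors. This reproduces the plan's 83.
- 83/(1 − 0.5) = 166 reproduces the recruitment figure.
- With 0.13 read as a correlation or standardised coefficient, N would be 614. As a partial R², N would be 73.

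So 83 reproduces only with f² = 0.13, which is a partial correlation of √(0.13/1.13) = 0.34.

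**2. Effect of leaving chronotype out.** The documents give no correlation of chronotype with mealtime or with glycaemia, so both are assumptions. Both are meant as what remains after the listed covariates, including sleep pattern and light exposure:

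- ρ, chronotype with last mealtime: 0.3-0.5
- b, chronotype with glycaemia: 0.13-0.20
- true mealtime effect: zero

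The induced mealtime-outcome correlation is r = ρ·b, with f² = r²/(1 − r²). The rejection rate follows from the same noncentral t at N = 83, taking p = 6 for the six listed covariate groups. Using 1 or 10 predictors changes the rates by less than 0.1 percentage point.

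| ρ | b | r = ρ·b | f² | Noncentrality √(83·f²) | False-positive rate |
|---|---|---|---|---|---|
| 0.3 | 0.13 | 0.039 | 0.00152 | 0.356 | 6.4% |
| 0.3 | 0.20 | 0.060 | 0.00361 | 0.548 | 8.4% |
| 0.5 | 0.13 | 0.065 | 0.00424 | 0.593 | 9.0% |
| 0.5 | 0.20 | 0.100 | 0.01010 | 0.916 | 14.8% |

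Outside this range, ρ = 0.2 with b = 0.1 gives 5.4%, and ρ = 0.5 with b = 0.3 gives 27.6%. The rate depends heavily on values that the documents do not supply. It also rises with N: if all 166 were evaluable, the last row of the table would be 25.1%. More recruitment does not remove the problem.

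**3. Price of adding chronotype.** If chronotype correlates ρ with mealtime given the other covariates, the mealtime interval widens by about 1/√(1 − ρ²), before any gain from smaller residual variance:

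- ρ = 0.3: 1/√0.91 = 1.05
- ρ = 0.5: 1/√0.75 = 1.15

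Power at 83 depends on what the planned f² meant.

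- If 0.13 was meant before chronotype adjustment, it becomes 0.13·(1 − ρ²), with p = 7. At ρ = 0.3 this is 0.118 and power is 0.87. At ρ = 0.5 it is 0.0975 and power is 0.80.
- If 0.13 was meant after adjustment, power stays at 0.90.

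**The case against.** **The listed covariates may already do part of the work.** The gloss of sleep pattern as duration belongs to a different model. The sleep questionnaire in Appendix H records bedtime, time to fall asleep and get-up time separately for weekdays and rest days, close to what the Munich questionnaire asks. Hourly light exposure is also adjusted for. This stands: some of the chronotype effect may be removed, and the correlations assumed above apply only to what is left. But the plan does not say which sleep items enter the night-meal model, and duration alone would not carry timing.

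**The confounder list may be open-ended.** The word for including can be read that way. But nothing commits the plan to chronotype, and an open list leaves the choice until after the data are seen.

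**Chronotype is not clearly upstream.** A reader might infer that chronotype is a fixed trait, so that only the adjusted coefficient matters. The documents do not support this. The synopsis makes change in chronotype at 6 months a secondary outcome. Section 3.2 says that life circumstance can modulate it. Section 3.1 and the framework text in the Introduction say that food intake and meal timing act on peripheral clocks. If meal timing shifts chronotype, adjustment removes part of the effect of interest. This stands, and it is why both estimates are needed.

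**The aim is stated as association.** That lowers the severity. It does not remove the need to say whether the two hypothesised associations are distinct.

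**Conclusion.** The point holds in a limited form. No listed model contains both chronotype and last night mealtime, so part of a late-meal association may reflect chronotype. Under the assumed correlations, and with no true mealtime effect, the false-positive rate at 83 is about 6-15% rather than 5%. The true size cannot be found from the documents, and with weak links the inflation is negligible.

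Three stronger readings are not supported:

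- **That a late-meal association is simply a chronotype association.** Sleep pattern and light exposure may absorb part of the effect, and the plan links evening type to later bedtime. Its link to later eating is implied, not quantified.
- **That the induced coefficient of 0.039-0.10 can be set against the planning value 0.13.** The plan calls 0.13 a β-coefficient, but it reproduces 83 only as f². The like-for-like comparator is the partial correlation of 0.34: 0.039/0.34 to 0.10/0.34 is about 11-29%.
- **That the mealtime-diabetes logistic model needs the same change.** The literature review (1.1 Prediabetes) gives yearly progression of 5.8-18.3%. Halved for 6 months, 83 × 0.029 = 2.4 to 83 × 0.0915 = 7.6, so about 2-8 events. That is too few to make a further covariate clearly supportable.

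This should be fixed, as a cheap improvement. It does not invalidate the study.

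**What to change.** In the Statistical Analysis section:

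1. Add baseline chronotype from the Munich questionnaire to the covariates of the night-meal generalized linear model.
2. Report the last-mealtime coefficient and its interval with and without chronotype.
3. State that a mealtime association independent of chronotype will be claimed only if the adjusted estimate supports it.
4. State that the adjusted estimate may be over-adjusted if meal timing itself shifts chronotype.

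Leave the diabetes logistic model as it is on this point.

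The data are already collected. The cost is a few sentences in the plan and one or two degrees of freedom. At the assumed correlations the mealtime interval widens by about 5-15%. Power at 83 falls from 0.90 to about 0.87-0.80 if the planned f² of 0.13 was meant before chronotype adjustment, and is unchanged if it was meant after. The plan should say which was meant.
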